#### run;

- ATRTN: Treatment group (placebo group [reference group], low-dose group, high-dose group)
   AVISITN: Time point (Week 12, Week24)
  - SUBJID: Patient ID

AVAL: Response variable

BASE: Baseline value

- Contrast coefficient (-2 1 1): Paired comparison of low-dose group saturation Contrast coefficient (-1 0 1): Paired comparison of linear trend Contrast coefficient (-1 -1 2): Paired comparison of high-dose group saturation
- # If convergence is not achieved with UN, TOEP will be used. If convergence is not achieved yet, the following will be used in this order:  $AR(1) \rightarrow CS \rightarrow VC$ .

## **10.** Appendix

	Table 10.1Method to Derive %MVI (%)
Evaluation of muscle volume	Method of derivation
%MVI (%) in right leg	Muscle in middle part (right surface area) / (muscle in middle part (right surface area) + fat in middle part (right surface area) - subcutaneous fat in middle part (right surface area)) × 100
%MVI (%) in left leg	Muscle in middle part (left surface area) / (muscle in middle part (left surface area) + fat in middle part (left surface area) - subcutaneous fat in middle part (left surface area)) × 100
%MVI (%) in both legs	Muscle in middle part (bilateral surface area) / (muscle in middle part (bilateral surface area) + fat in middle part (bilateral surface area) - subcutaneous fat in middle part (bilateral surface area)) × 100

#### Table 10.2 Method to Derive Pharmacodynamic Endpoints and Exploratory Endpoints

Pharmacodynamic and exploratory endpoints	Method of derivation
Urine tetranor-PGDM/Cre concentration ratio (ng/mg creatinine)	$PGDM^{\dagger} / Cre^{\dagger}$
Total urinary tetranor-PGDM excretion (ng)	PGDM <math>\dagger</math> × urine volume (mL)
Urinary tetranor-PGEM/creatinine concentration ratio (ng/mg creatinine)	$PGEM^{\dagger} / Cre^{\dagger}$
Total urinary tetranor-PGEM excretion (ng)	$PGEM^{\dagger} \times urine volume (mL)$
Urinary creatinine excretion (g)	$Cre^{\dagger} \times urine volume (mL)$
Urinary creatine excretion (g)	$Cr^{\dagger} \times urine volume (mL)$
% creatine in urine (%)	Urinary creatine excretion (g) / [Urinary creatine excretion (g) + Urinary creatinine excretion (g)] $\times$ 100

†PGDM: Urinary tetranor-PGDM concentration (ng/mL)
PGEM: Urinary tetranor-PGEM concentration (ng/mL)
Cre: Urinary creatinine concentration (g/mL)
Cr: Urinary creatine concentration (g/mL)

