## **6.3** Analyses of Pharmacodynamic and Exploratory Endpoints

The following analyses will be performed for urinary excretion of tetranor-PGDM/-PGEM, urine tetranor-PGDM/Cre concentration ratio, urine tetranor-PGEM/Cre concentration ratio, urinary creatinine excretion, urinary creatine excretion, and creatine in urine (%) in the PPS and FAS: Analysis will also be conducted in the group combining the low-dose group and the high-dose group excluding the analysis of MMRM and charts.

For the method to derive each endpoint, refer to Table 10.2. Method to Derive Pharmacodynamic Endpoints and Exploratory Endpoints.

- Summary statistics at each time point will be calculated for each treatment group.
- Summary statistics of the change rate from baseline at each time point will be calculated, followed by a 2-sample t-test between each treatment group and placebo group at each time point. If the data at Week 24 are missing, conduct analyses with and without the LOCF imputation.
- With respect to the above 2 analyses, subgroup analysis of the following items will be conducted for urinary tetranor-PGDM/creatinine concentration ratio in the PPS.
  - Subgroup analysis: Baseline 6MWD (<350 m, and  $\geq 350 \text{ m}$ )
- The treatment effect will be estimated using the MMRM. The changes from baseline in the values measured at other time points will also be included in this analysis. Covariates will be the assigned group, baseline value, time point, and the interaction term of the assigned group and time point.
- Using the MMRM, the dose relationship will be analyzed with treatment contrasts of (placebo group, low-dose group, high-dose group) = (-2 1 1), (-1 0 1), and (-1 -1 2). Covariates will be the assigned group, baseline value, time point, and the interaction term of the assigned group and time point.
- With respect to the above 2 analyses, subgroup analysis of the following items will be conducted for urinary tetranor-PGDM/creatinine concentration ratio in the PPS.
  - Subgroup analysis: Baseline 6MWD (<350 m, and  $\geq 350 \text{ m}$ )
- The correlation coefficients (Pearson and Spearman) with the change from baseline in each item specified in (1) and (2) of Section 6.2.1 will be calculated for the change rate from

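### SAP Table 10.2 labels the PGDM/creatinine and PGEM/creatinine ratios ng/mg, but its formulas and footnote units give ng/g, a factor of 1000

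*SAP*

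**What the plan says.** SAP section 6.3 sends the reader to Table 10.2 for the derivation of every pharmacodynamic and exploratory endpoint, so that table is the governing specification.

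Two of its rows are creatinine ratios: "Urine tetranor-PGDM/Cre concentration ratio (ng/mg creatinine" and "Urinary tetranor-PGEM/creatinine concentration ratio (ng/mg creatinine". Their formulas are PGDM / Cre and PGEM / Cre, with no conversion factor. The footnote defines the inputs: "PGDM: Urinary tetranor-PGDM concentration (ng/mL", "PGEM: Urinary tetranor-PGEM concentration (ng/mL" and "Cre: Urinary creatinine concentration (g/mL".

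A third row, "Urinary creatinine excretion (g", uses the same Cre and multiplies it by urine volume in mL.

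Section 6.3 then uses the ratios in two forms. The measured values are tabulated ("Summary statistics at each time point will be calculated for each treatment group") and plotted over time. The relative changes are tabulated and tested between groups ("Summary statistics of the change rate from baseline at each time point will be calculated"). SAP section 6.6 also enters the baseline PGDM/creatinine ratio as an explanatory variable in two analyses of covariance, one for change in 6MWD and one for change in %MVI.

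**The concern.** The label and the formula in each ratio row cannot both be right given the footnote units. A programmer who divides the two numbers as the table instructs will print values in ng/g under a heading that says ng/mg.

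At stake is the absolute level of two of the four pharmacodynamic endpoints listed in protocol section 2.4.3. The protocol treats urinary tetranor-PGDM as its marker of PGD2 production (section 1.1). Anyone comparing the tabulated ratios with another data set would be misled by three orders of magnitude.

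**Working it through.** **Inputs.** Row labels, formulas and footnote units all come from SAP Table 10.2. The documents give no concentrations, so the numerical illustrations below rest on assumed values and are marked as such.

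**Step 1: units of every row, using the footnote as written.**

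| Row | Labelled unit | Formula in units | Result | Agrees? |
|---|---|---|---|---|
| PGDM/Cre ratio | ng/mg | (ng/mL) / (g/mL) | ng/g | No |
| PGEM/Cre ratio | ng/mg | (ng/mL) / (g/mL) | ng/g | No |
| Total PGDM excretion | ng | (ng/mL) × mL | ng | Yes |
| Total PGEM excretion | ng | (ng/mL) × mL | ng | Yes |
| Creatinine excretion | g | (g/mL) × mL | g | Yes |
| Creatine excretion | g | (g/mL) × mL | g | Yes |
| % creatine in urine | % | g / (g + g) × 100 | % | Yes |

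Five of the seven rows agree with the footnote and the two ratio rows do not.

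**Step 2: size.** 1 g = 1000 mg, so 1 ng/mg = 1000 ng/g. The number produced by the formula is 1000 times the number in the labelled unit, whatever the inputs.

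Illustration (assumed PGDM 10 ng/mL, creatinine 0.5 mg/mL = 0.0005 g/mL):
- as written: 10 / 0.0005 = 20,000
- in ng/mg: 10 / (0.0005 × 1000) = 20

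Over an assumed range of PGDM 1 to 50 ng/mL and creatinine 0.0002 to 0.002 g/mL:
- as written: from 1 / 0.002 = 500 to 50 / 0.0002 = 250,000
- in ng/mg: 0.5 to 250

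**Step 3: could the footnote unit simply be mg/mL?** The ratio rows would then be right, but creatinine excretion would be (mg/mL) × mL = mg under a label of g. With an assumed 800 mL of urine:
- Cre in g/mL: 0.0005 × 800 = 0.4 g, as labelled
- Cre in mg/mL: 0.5 × 800 = 400, which is mg but labelled g

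No single unit for Cre satisfies both the ratio rows and the excretion row without a conversion factor. A letter lost from the footnote therefore cannot explain the mismatch.

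**Step 4: is a conversion given elsewhere?** Neither document gives one. The SAP does write out a unit conversion where it intends one: section 6.2.2 (3) converts magnesium from mEq/L to mg/dL with an explicit factor of 1.2.

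**Step 5: which outputs change.** Let the programmed ratio be R' = 1000 × R.

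- *Measured-value summaries and time-course plots (section 6.3):* these show R' and are 1000 times too large in the labelled unit.
- *Change rate from baseline:* (R'₂ − R'₁) / R'₁ = (R₂ − R₁) / R₁, because the factor cancels. With assumed PGDM of 5 then 4 ng/mL at 0.0005 g/mL, the values are 10,000 to 8,000 as written, or 10 to 8 in ng/mg. Both give −20%. The t-tests, summaries and plots of change rates are unaffected, as are correlations based on them.
- *Analyses of covariance (section 6.6):* βR = (β/1000)R', so the coefficient for the baseline PGDM ratio is 1000 times too small per labelled unit. Its p-value, the model fit and all other coefficients stay the same.
- *MMRM (sections 6.3 and 8.3):* estimates and confidence limits scale by 1000 only if the response is absolute change, and p-values do not move. Section 6.3 speaks of changes from baseline for this model but of change rates for the t-tests. The SAS code in section 8.3 identifies AVAL only as the response variable, so the SAP does not settle which applies.

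**The case against.** The strongest reply is that the table is incomplete rather than wrong. It prints both the input units and the output unit. Read as an equation between physical quantities, PGDM / Cre is the right ratio: 20,000 ng/g and 20 ng/mg are the same amount. The error appears only if someone divides the bare numbers and ignores the label beside them. Creatinine is measured at the sites (protocol sections 8.2 and 8.4.3), and neither document says in which unit it is supplied or how units are handled on transfer. The layout of tables and figures is left to a separate report analysis plan (SAP section 8.2). A constant factor also distorts no comparison between groups or visits, and the study is exploratory, with a sample size set by feasibility.

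Part of this stands. The mismatch is certain, but whether it reaches the outputs depends on how the derivation is programmed. The consequence is one of reporting scale. The covariance coefficient belongs to an adjustment variable, and the MMRM effect is conditional on a separate ambiguity, so neither adds much weight.

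The reply does not remove the point. A derivation table exists so that a programmer can follow it literally. Followed literally, this one gives numbers that contradict its own labels, and no reading of the footnote makes all seven rows agree. An unknown site unit is a further reason for the table to be explicit.

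**Conclusion.** The concern holds. Both ratio rows are mislabelled by a factor of exactly 1000 relative to their own formulas and input units. That factor needs no assumption about concentrations. The appearance of the error in reported results rests on one assumption: that the formulas are programmed as written with creatinine in g/mL.

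On that assumption, the absolute levels of two of the four pharmacodynamic endpoints are misreported. No treatment comparison of change rates, no p-value, no total-excretion or exploratory endpoint, and no part of the primary 6MWD analysis is altered. It should be corrected before the outputs are produced, but it does not threaten the study's conclusions.

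**What to change.** Amend the two ratio rows of SAP Table 10.2 in one of two ways, leaving Cre in g/mL for the excretion rows:

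1. Write the formulas as PGDM / (Cre × 1000) and PGEM / (Cre × 1000), keeping the ng/mg creatinine label. This keeps the unit the SAP chose.
2. Keep the formulas and relabel both rows ng/g creatinine. This changes the reporting unit. The protocol gives no unit for the Phase I ratios, so the effect on comparability with that study cannot be judged from these documents.

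The first is the simpler choice. Either costs one edit to two rows and needs no change to data collection or to any analysis method. It would help to state in the same footnote the unit in which the sites supply creatinine and any conversion applied on receipt.
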